7.7.3 Other concomitant treatment

Other medication other than that described above, which is considered necessary for the patient's safety and well-being, may be given at the discretion of the investigator and recorded in the appropriate sections of the eCRF.

8. STATISTICAL ANALYSES BY ASTRAZENECA

8.1 Statistical considerations

All personnel involved with the analysis of the study will remain blinded until database lock and protocol violators identified at the end of the 28-week randomized treatment period. AstraZeneca and its applicable representative(s) will be unblinded in Extension Periods 1 and 2 (ie, from Week 28 onwards). Sites, site monitors, and patients will remain blinded during Extension Periods 1 and 2.

Statistical analysis of this study will be the responsibility of AstraZeneca or its representatives.

All of the data will be entered, verified, and archived by AstraZeneca or its representatives. All data listings, summaries, and analyses will be performed under the guidance and approval of statisticians at AstraZeneca.

Baseline: Baseline refers to the last measurement collected prior to the first dose of study medication at the randomization visit.

All collected data will be listed. A detailed statistical analysis plan (SAP) will be written and approved prior to database lock.

8.2 Sample size estimate

A total of 209 patients per treatment group are required, assuming:

- Mean difference of 0.35% in HbA1c change from baseline with EQW + dapagliflozin versus each monotherapy
- Standard deviation of 1.1% and 90% power (based on a 2-sample t-test at a 0.05 significance level)

Assuming a 5% drop-out rate prior to Week 4 (Visit 6), the first visit where HbA1c is tested, 220 patients per treatment arm (a total of approximately 660 patients) would have post-baseline measurements of HbA1c and thus be included in the ITT analysis of the primary objective. Assuming 40% screen failure, a total of 1100 patients will be screened.

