3.3.1 Procedures for randomization

Patients who meet all study requirements based on inclusion and exclusion criteria will be centrally randomized (ie, not at the site level or not in a block-stratified fashion) to 1 of 3 treatment groups in a 1:1:1 ratio at Visit 3 (Randomization visit) by the IVRS/IWRS:

- EQW 2 mg + dapagliflozin 10 mg
- EQW 2 mg + placebo
- Dapagliflozin 10 mg + placebo.

Randomization will be stratified by baseline HbA1c stratum ($<9.0\%$ or $\geq 9.0\%$) (refer to Section 3.5); the randomization schedule will be generated according to the stratifying factor. Randomization codes will be assigned strictly sequentially as patients become eligible for randomization.

Specific information concerning the use of the IVRS/IWRS will be provided to the investigators. If a patient is discontinued from the study, his/her randomization or enrollment number will not be reused, and the patient will not be allowed to re-enter the study. Randomized patients who discontinue early from the study will not be replaced.

If a randomization number is allocated incorrectly, no attempt should be made to remedy the error once study material has been dispensed. The patient will continue with the allocated number and study material. AstraZeneca or representative should be notified as soon as the error is discovered. Subsequent patients will continue using the first unallocated randomization number in the original numbering sequence.

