8.5 Methods for statistical analyses

8.5.1 Analysis of the primary variable

The primary analysis will assess the benefit (superiority) of the combination of EQW + dapagliflozin over the individual components (ie, over EQW and over dapagliflozin) for the change in HbA_{1c} from baseline to Week 28 of the short-term double-blind treatment period for the ITT population.

The mixed model for the repeated measures (MMRM) will include change from baseline to Week 28 in HbA_{1c} as the dependent variable, treatment, region, baseline HbA_{1c} stratum ($<9.0\%$ or $\geq 9.0\%$), week, and treatment by week interaction as fixed factors. Baseline measurement of HbA_{1c} will be included as a continuous covariate. All observed HbA_{1c} values from post-baseline (including early dropouts, but excluding those data points after glycemic rescue therapy or post-treatment follow-up) will be included in the MMRM analysis. Since MMRM will be used for the primary analysis of primary endpoint, there will be no need

to impute missing data. Consequently, no Last Observation Carried Forward or other imputation technique will be required or used for the primary analysis. An unstructured covariance matrix will be used for the MMRM analysis, unless the model does not converge, in which case the covariance structure will be decided based on model convergence status and the Akaike information criterion. The least-squares (LS) means, standard errors, and 2-sided 95% confidence intervals, as well as the mean difference between treatment groups (EQW + dapagliflozin compared to EQW and compared to dapagliflozin) will be presented.

The treatment comparison of the primary efficacy endpoint (HbA1c change from baseline) will be considered significant if and only if the comparisons of the combination treatment group (EQW + dapagliflozin) against both of the 2 active-control groups (dapagliflozin 10 mg QD and EQW 2 mg) are significant. Due to this specific criterion for showing superiority of the combination treatment group over the individual treatment groups in primary endpoint, no multiplicity adjustment for the primary analysis will be required to control the overall type-I error, which is considered to be 0.05; consequently, both of the individual treatment comparisons will be performed at 5% level of significance (ie, $\alpha = 0.05$ 2-sided).

The same MMRM analysis will be applied to the PP population as a supportive analysis for the primary efficacy endpoint.

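### The 90% power in Section 8.2 is for one pairwise comparison; the trial's own success rule needs both, and for that the planned size gives about 83%

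*Protocol*

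**What the plan says.** Section 8.2 (Sample size estimate) and the matching part of the synopsis give the sizing. "A total of 209 patients per treatment group are required, assuming" two things: "Mean difference of 0.35% in HbA1c change from baseline with EQW + dapagliflozin versus each monotherapy", and "Standard deviation of 1.1% and 90% power (based on a 2-sample t-test at a 0.05 significance level"). The number is then adjusted for early loss. The assumption made reads "Assuming a 5% drop-out rate prior to Week 4 (Visit 6), the first visit where HbA1c is tested". From this the protocol concludes that "220 patients per treatment arm (a total of approximately 660 patients) would have post-baseline measurements of HbA1c", which places them in the ITT analysis of the primary objective.

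Section 3.3.1 allocates patients "to 1 of 3 treatment groups in a 1:1:1 ratio at Visit 3 (Randomization visit) by the IVRS/IWRS".

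Section 8.5.1 defines success on the primary endpoint. It is met if and only if the comparisons of the combination "against both of the 2 active-control groups (dapagliflozin 10 mg QD and EQW 2 mg) are significant". Because of that rule no multiplicity adjustment is made, and "both of the individual treatment comparisons will be performed at 5% level of significance", two-sided. Section 8.5.2 opens the 7 secondary endpoints (13 comparisons) only when both primary comparisons have succeeded.

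The protocol gives no power for the rule that both must succeed.

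**The concern.** The protocol uses the both-must-win rule to justify testing each comparison at the full 5%. The same rule has a price in power, and Section 8.2 does not report it. The sizing rests on a single two-group test, whereas the primary objective is decided by two tests that must both succeed. Since the protocol assumes the same 0.35% against each comparator, neither test can be treated as certain to succeed, and the chance of winning both is lower than the chance of winning either one.

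The joint criterion is the only route to a positive primary result and the gate to all formal secondary testing. A reader of the synopsis will naturally take 90% as the probability of meeting the primary objective. If that probability is materially lower, the sponsor and the ethics committees are judging the design on a figure that does not apply to it.

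**Working it through.** **Inputs**
- True difference d = 0.35% against each monotherapy; SD = 1.1%; 2-sample t-test at 0.05; 209 per group; 5% drop-out (Section 8.2).
- Two-sided 0.05 for each comparison, both required (Section 8.5.1).
- Three arms, 1:1:1 (Section 3.3.1).
- Correlation of the two test statistics: 0.5. This is derived, not stated. Both contrasts share the combination arm, and with equal n and equal SD their covariance is SD²/n and each variance is 2·SD²/n, so the ratio is 1/2.

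**1. Reproduce the protocol's figures**
- Normal approximation: n = 2(1.960 + 1.282)² × 1.1² / 0.35² = 207.6, so 208. The noncentral t solution is 208.54, so 209. This matches.
- A one-sided test would need only 170, so the calculation is two-sided.
- 209 / 0.95 = 220 per arm, 660 in total. This matches, and it shows that 220 is the number before drop-out and 209 the number evaluable.

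**2. Power of one comparison at 209 per arm**
- SE = 1.1 × √(2/209) = 0.1076; d/SE = 3.253; 3.253 − 1.960 = 1.293.
- Φ(1.293) = 90.2% (normal); 90.1% (noncentral t).

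The stated 90% is therefore the power of a single comparison.

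**3. Power of the success rule**

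Joint power = P(Z1 > 1.960 and Z2 > 1.960), where Z1 and Z2 are bivariate normal with means d1/SE and d2/SE, unit variances and correlation 0.5.

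| Evaluable per arm | One comparison (t) | Both, normal | Both, simulated t-tests |
|---|---|---|---|
| 209 | 90.1% | 83.5% | 83.4% |
| 220 | 91.5% | 85.7% | 85.5% |

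The simulations used 400,000 runs. If the two tests were wrongly treated as independent, the figure at 209 would be 0.902² = 81.3%, so the shared arm helps, but only by about 2 points.

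Risk of missing the primary criterion at 209: 100 − 83.4 = 16.6%, about 17%.

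**4. Sensitivity at 209 per arm (normal approximation)**

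| True differences | Joint power |
|---|---|
| 0.35% and 0.35% | 83.5% |
| 0.35% and 0.45% | 89.5% |
| 0.35% and 0.70% | 90.2% |
| 0.38% and 0.38% | 89.9% |

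With one difference held at 0.35%, joint power cannot exceed the power of that comparison, about 90%.

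**5. Size needed for 90% joint power under the protocol's assumptions**
- 248 evaluable per arm (joint power 90.1%); 248 / 0.95 = 261.1, so 262 randomized per arm, 786 in total. This shows the size of the gap and is not a proposal to enlarge the trial.

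**The case against.** The strongest reply is that Section 8.2 never claims joint power. It names a 2-sample t-test and states the effect against each monotherapy, so read narrowly its 90% is correct, and the protocol nowhere prints a 10% risk of failure. That is fair as to the arithmetic: 209 and 220 are both right for one comparison. It does not rescue the statement. The same section says this number is required and ties it to the analysis of the primary objective, which is decided by both tests together. The only power reported is for an event that the protocol does not count as success.

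Four further points deserve weight.

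- **220 or 209.** Section 8.2 literally says 220 per arm would have post-baseline HbA1c. On that reading joint power is about 85.5%, not 83%. Since 220 = 209 / 0.95, 209 evaluable is the likelier intent, and neither reading reaches 90%.
- **Model.** The primary analysis is an MMRM adjusting for baseline HbA1c, stratum and region. If 1.1% is an unadjusted SD, which the protocol does not say, a residual SD of about 1.01% would give 90% joint power at 209. Against this, loss of data after Week 4 and the exclusion of post-rescue values lower power. The protocol quantifies neither, so neither can be relied on. The corrected sentence should name the t-test as its basis.
- **Sensitivity.** The shortfall is sensitive to the assumed effect: two true differences of 0.38% instead of 0.35% bring joint power to about 90%. But the protocol assumes 0.35%.
- **Consequence.** Nothing in the analysis, the type I error control or the conclusions would change. This stands: the point concerns a misdescribed planning figure, not the validity of the trial.

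**Conclusion.** The concern holds. Under the protocol's own assumptions (0.35% against each monotherapy, SD 1.1%, two-sided 0.05 per test, 1:1:1 allocation), 209 evaluable patients per arm give 90.1% power for each comparison and 83.4% (simulated t-tests) to 83.5% (normal) for the criterion in Section 8.5.1. The stated 90% does not apply to that criterion, whether 209 or 220 per arm are evaluable. At 209 the joint figure lies between about 83% and 90% when one difference is 0.35% and the other is that or larger.

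The result depends on equal SDs and arm sizes (hence the correlation of 0.5) and on two unadjusted t-tests. Any precision gained from the MMRM, or information lost after Week 4, would move it by an amount that the protocol does not give.

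**What to change.** In Section 8.2 and the synopsis, replace the single power statement with one along these lines: *209 evaluable patients per arm give 90% power for each pairwise comparison and, on the basis of two 2-sample t-tests sharing the combination arm, about 83% power for the primary success criterion (both comparisons significant) when both true differences are 0.35% and the SD is 1.1%; if one difference is larger, joint power rises to at most about 90%.*

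In the same edit, make clear that 220 per arm is the number randomized and 209 the number expected to have a post-baseline HbA1c, so that the power figures have a definite base.

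The cost is a sentence or two in each place and a less favourable headline figure. Enrolment, conduct, the analysis model and the testing rules stay as they are.

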8.3 Definitions of analysis sets

8.3.1 Efficacy analysis set

There will be 2 analysis sets for the efficacy evaluation:

- Intent-to-treat (ITT), the primary analysis set will include randomized patients who receive at least 1 dose of study medication and have at least 1 post-baseline HbA1c assessment.
- Per-protocol (PP), the secondary analysis set, will be a subset of the ITT population through the exclusion of those with important protocol violation(s). Important protocol violations are those that have the potential to affect the result of the primary analysis. Detailed exclusion criteria for the PP population will be specified in the SAP. Patients excluded from the PP analysis will be identified before database lock.

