1.3.1 Ethical Safety Considerations

EQW has not previously been studied in combination with dapagliflozin. EQW may cause nausea due to delayed gastric emptying, an effect that tends to resolve over time, and dapagliflozin results in a mild osmotic diuresis. Both agents are associated with a modest systolic blood-pressure-lowering effect of approximately 2 to 4 mmHg. In addition, there have been reports of hypovolemia and prerenal azotemia with both agents, though the incidence of these events has been low. Since the combination of the 2 agents may potentially increase the risk of these events, investigators should be alert to signs or symptoms of these conditions. Blood pressure and renal function will be monitored at each study visit.

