The following will be performed during these visits:

- IVRS will be contacted to register the visit.
- AEs, potential CV event triggers (Section 6.8.1), and concomitant medications will be reviewed.
- A brief physical exam will be conducted (refer to Section 5.2.2).

- Vital signs (sitting systolic and diastolic BP and HR) will be assessed.
- Body weight will be measured.
- Blood samples will be collected **prior to administration of study medication** for the following assessments:
 - Chemistry and hematology
 - HbA1c (Visits 6, 7, 8, 9, 10, and 11 only)
 - Fasting plasma glucose will be collected at all treatment visits (need for rescue will be evaluated at Visits 7 to 11 only)
 - Serum creatinine (calculated creatinine clearance; Cockcroft-Gault formula)
 - Serum antibodies to exenatide (Visits 6, 7, 8, and 10 only)
 - Plasma exenatide and dapagliflozin (Visits 6, 7, 8, and 10 only).
- Urine will be collected for the following assessments:
 - Urinalysis
 - Urine glucose/creatinine ratio
 - Pregnancy test for all female patients, unless patient has had a hysterectomy.
- Patient diary will be reviewed.
- Visit 11 only: Patients will be instructed to perform 6-point SMBG on any 3 days in the week prior to Visit 12.
- Hypoglycemia episodes will be assessed.
- Diet and exercise counseling will be provided.
- Glucose meter and supplies will be provided.
- Study medication compliance will be reviewed.
- Study medication will be dispensed every 4 weeks during the treatment period: Visits 6 to 11. Study site personnel will monitor administration of injectable study medication (if the patient is due for an injection at the time of the visit).

- Instructions, reminders, and supplies (as appropriate) will be given to the patient (or designated caregiver) for proper transportation and storage of the study medication (to ensure temperature control, etc.).
- Rescue medication will be dispensed at Visits 7 to 11 if criteria for rescue medication are met (refer to [Table 3](#)).
- Used/unused study medication will be collected every 4 weeks (Visits 6 to 11).

4.2.2 End of Treatment Period Visit (Visit 12, Week 28) or Early Termination or Rescue during Treatment Period

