8.5.2 Analysis of the secondary variables

For the secondary efficacy endpoints, a Cochran-Mantel-Haenszel (CMH) test stratified by baseline HbA1c stratum ($<9.0\%$ or $\geq 9.0\%$) will be applied to the categorical variables, and an MMRM model or analysis of covariance (ANCOVA) model will be applied to the continuous variables.

The significance or non-significance of the treatment comparisons for the primary efficacy endpoint will determine whether or not the statistical tests are to be performed to compare treatments for the secondary efficacy endpoints. In other words, if and only if the superiority of the combination treatment group is established simultaneously over both the individual treatment groups in primary endpoint at 5% level of significance, only then can the analyses of the set of 7 secondary endpoints be performed at 5% level of significance. In order to control the overall type-I error rate at 5% level of significance, multiplicity adjustment will be applied while analyzing the set of secondary endpoints, details of which will be provided in the SAP prior to unblinding of treatment assignments.

The 7 secondary endpoints are listed below:

- Change in total body weight from baseline to Week 28
- Change in FPG from baseline to Week 28
- Change from baseline in 2-hour PPG after standardized MTT at Week 28
- Proportion of patients achieving HbA1c $<7.0\%$ at Week 28

- Proportion of patients achieving weight loss ≥ 5 .0% at Week 28
- Change from baseline in FPG to Week 2 (dapagliflozin+exenatide vs exenatide)
- Change from baseline in seated systolic BP from baseline to Week 28

Although the nominal p-values respective to each of the treatment comparisons for all the 7 secondary endpoints will be presented in the report, in order to control the overall type-I rate at 5% level of significance, multiplicity adjustment will be applied while performing the 13 treatment comparisons in the set of 7 secondary endpoints, details of which will be provided in the SAP prior to unblinding of treatment assignments.

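### The ITT set requires a post-baseline HbA1c, so treated patients with none at any visit drop out of the Week 2 FPG analysis and the responder denominators

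*Protocol*

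**What the plan says.** Section 8.3.1 (repeated in the synopsis) states: "There will be 2 analysis sets for the efficacy evaluation". The primary one, ITT, consists of "randomized patients who receive at least 1 dose of study medication and have at least 1 post-baseline" HbA1c value. The second, per-protocol, is drawn from within ITT. Only its exclusion criteria are left to the SAP; the ITT definition is fixed in the protocol.

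On timing, section 4.2.1 lists "HbA1c (Visits 6, 7, 8, 9, 10, and 11 only" among the treatment-visit blood samples, so HbA1c starts at Week 4. FPG is drawn at every treatment visit, and Table 1 also has weight and blood pressure at Weeks 1 and 2. Section 8.2 links the set to this schedule: "Assuming a 5% drop-out rate prior to Week 4 (Visit 6), the first visit where HbA1c is tested".

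Sections 8.4.2 and 8.5.2 list seven secondary endpoints under multiplicity control. One is "Change from baseline in FPG to Week 2 (dapagliflozin+exenatide vs exenatide"). Two others are proportions at Week 28, HbA1c <7.0% and weight loss of at least 5%, tested by a stratified CMH test. No separate analysis set is named for any of these.

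HbA1c is also collected outside the regular schedule. Under section 3.9.1, patients who permanently stop study medication have an Early Termination visit with the Week 28 assessments and are asked back at Week 28. Table 1 and section 4.2.2 include HbA1c at both visits.

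**The concern.** Membership of the main efficacy set depends on an event after randomization, and that event is specific to HbA1c. Two consequences follow for endpoints other than the primary.

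First, Week 2 FPG is complete before the first scheduled HbA1c. A patient who gives that sample and then leaves with no later HbA1c has the endpoint observed, yet is not in its analysis.

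Second, for the two responder endpoints, a treated patient who leaves early without an HbA1c disappears from the denominator. A missing-data rule in the SAP, applied to this set, cannot restore patients whom the set has already removed. Weight loss of at least 5% does not involve HbA1c at all.

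At stake are modestly overstated responder rates and, if such losses differ between arms, a distorted treatment difference. Section 1.3.1 gives a reason why they might differ: "EQW may cause nausea due to delayed gastric emptying, an effect that tends to resolve over time". The dapagliflozin + placebo arm receives no EQW.

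**Working it through.** **The protocol's own figures (section 8.2).** Inputs: difference 0.35%, SD 1.1%, two-sided alpha 0.05, power 90%.
- The two-sample t-test needs 208.54, so 209 per group. This matches the protocol.
- Allowing 5% drop-out: 209 / 0.95 = 220 per group, 3 × 220 = 660. This also matches.
- The 220 is therefore the number randomized, and 209 (220 × 0.95) is the number expected to have a post-baseline HbA1c. The sentence in 8.2 attaches the post-baseline measurements to the 220.

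**How many patients the HbA1c condition can remove.**
- Per arm: 220 × 0.05 = 11. In total: 660 × 0.05 = 33.
- This is an upper figure under the 5% allowance. Anyone who stops before Week 4 but gives an HbA1c at Early Termination or at the Week 28 return visit stays in the set, and anyone never dosed is excluded under either definition.
- For Week 2 FPG the comparison involves two arms, so at most 2 × 11 = 22 patients, and only those among them who reached the Week 2 visit.

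**Effect on the primary analysis.** Power is 90.1% at 209 per group and would be 91.5% at 220 if all had HbA1c data. The excluded patients have no HbA1c outcome to contribute to the MMRM, so power stays at about 90% with or without them in the set.

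**Effect on responder rates.** The documents give no responder rates and no early loss by arm, so these inputs are assumptions. If excluded patients count as non-responders, the rate in all treated patients is the rate among those kept × (1 − fraction excluded).
- 45% kept, 5% excluded: 0.45 × 0.95 = 0.4275, or 42.8%. The set overstates the rate by 2.25 points.
- 45% kept in both arms, 8% vs 2% excluded: 0.45 × 0.92 = 0.414 and 0.45 × 0.98 = 0.441. The set shows no difference; all treated patients show 2.7 points.

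Range for an assumed 40% (combination) vs 25% (control) among those kept, a 15.0-point difference in the current set:

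| Excluded, combination vs control | All treated, combination | All treated, control | Difference |
|---|---|---|---|
| 5% vs 5% | 0.40 × 0.95 = 38.0% | 0.25 × 0.95 = 23.75% | 14.25 points |
| 8% vs 2% | 0.40 × 0.92 = 36.8% | 0.25 × 0.98 = 24.5% | 12.3 points |
| 2% vs 8% | 0.40 × 0.98 = 39.2% | 0.25 × 0.92 = 23.0% | 16.2 points |

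The current set can thus overstate or understate the advantage, depending on which arm loses more.

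**The case against.** The strongest reply is that the protocol already works to obtain an HbA1c from early leavers. Section 3.9.1 provides the Early Termination visit and the Week 28 return, section 3.10 sends withdrawn patients through the same procedures, and patients lost to follow-up are pursued for the Early Termination visit. A reader might infer that everyone lost before Week 4 is removed from the efficacy analyses. The documents do not support that: any post-baseline HbA1c is enough. It also means that the 5% in section 8.2 is a sample-size allowance, not a forecast of treated patients without HbA1c. This part stands and limits the size of the problem. It does not remove it, because inclusion then depends on attending a later visit, which is itself a post-randomization event.

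A reader might also infer that early EQW nausea biases the Week 2 FPG comparison. It gives no clear reason to expect that, since both arms in that comparison receive EQW; the harm there is discarded data. The same applies to combination vs EQW on the responder endpoints. Differential loss from nausea is plausible only for combination vs dapagliflozin, and a patient who stops because of nausea is the kind of patient the Early Termination visit is meant to capture.

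Nor does the set create a spurious 2.7-point difference. In that example it shows equal rates and would hide the difference.

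Finally, rules for missing responder data commonly belong in the SAP, which is not at hand, and analysing every patient with data for a continuous endpoint still conditions on data observed after randomization. Both points are fair. But the denominator to which any SAP rule would apply is set here in the protocol, and the change at least stops observed values being discarded because a different variable is missing.

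**Conclusion.** The point holds for treated patients with no post-baseline HbA1c at any visit. Neither efficacy set retains them, so their Week 2 FPG values are lost and they leave both responder denominators.

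The effect is modest and falls on secondary endpoints: at most about 11 per arm if the 5% allowance is right, about 2.25 points on a 45% responder rate, and roughly 1 to 3 points on a treatment difference if exclusion is unequal. The responder rates and the 8% vs 2% split are assumptions, and no documented figure shows that early loss will differ between arms. The conclusion for the primary HbA1c comparison does not depend on this. The definition is still worth changing, because the loss is avoidable and the affected endpoints are part of the confirmatory secondary family.

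**What to change.** In section 8.3.1 and the synopsis, define the primary efficacy set as all randomized patients with at least one dose of study medication, with no HbA1c condition. Section 8.3.2 already defines this population for safety. Then state that:
- MMRM and ANCOVA analyses use every patient in the set with data for the endpoint concerned;
- CMH analyses keep all treated patients in the denominator, with missing responder status counted as non-response.

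Reword section 8.2 so that 220 per arm is the number randomized and 209 the number expected to have post-baseline HbA1c.

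The cost is wording only, before unblinding for the Week 28 analysis. No new data or patients are needed, the sample size stands, and the HbA1c MMRM is essentially unchanged. The one downside is slightly lower reported responder rates.
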